8.4.6. Pregnancy

The investigator should notify the Sponsor immediately regarding a pregnancy in a (1) female clinical trial patient or (2) female partner of a male clinical trial patient.

Pregnant female patients must be withdrawn from study drug.

If a female partner of a male patient becomes pregnant or suspects she is pregnant by the male patient, the male patient will be advised by the study Investigator to have his female pregnant partner inform her treating physician immediately.

The Investigator must perform medical assessments as clinically indicated and continue to follow the patient for ≥ 4 weeks after delivery. Medical details for both the mother and baby must be obtained.

The Investigator must complete a study-specific Pregnancy Form upon confirmation of a pregnancy. Pregnancy reporting forms will be provided to the site.

8.4.7. Hypersensitivity Reactions

Patients experiencing any hypersensitivity reaction should receive appropriate symptomatic medical care, as needed. Patients should be instructed to inform the site if a hypersensitivity reaction occurs. At the next study visit, a blood sample must be collected for immunogenicity analysis. The Sponsor or designee should be immediately consulted, particularly if the hypersensitivity reaction might be attributed to the study drug, and particularly if the reaction is severe, for discussions about discontinuing the study medication.

8.5. PK and ADA Sampling

Serum PK and ADA samples will be collected in all patients. Positive ADA results may be further evaluated for neutralizing antibodies (nAB). The procedural instructions will be provided in a separate PK and Serum Antibody Sampling manual.

8.6. Study Termination

The Sponsor has the right to terminate the study at any time. Should the study be terminated, the decision and reason will be communicated in writing by the Sponsor to the Investigator and request that all patients be discontinued. Patients should be scheduled for an Early Termination visit. The entire study will be stopped if:

- Evidence has emerged that, in the collective opinion of the Investigators at each site with the concurrence of the Sponsor, or the sole opinion of the Sponsor, continuation of the study is unnecessary or unethical
- The stated objectives of the study are achieved
- The Sponsor discontinues the development of the study drug

All data available for the patient at the time of study discontinuation must be recorded in the patient's records and the eCRF.

8.6.1. Early Termination of Study Patients

The Investigator will make reasonable efforts to keep each patient in the study. However, patients may terminate or be terminated early from the study for the following reasons:

- Voluntarily withdrawal of consent to participate in the study participation, at any time
- Adverse event, laboratory abnormality or inter-current illness which, in the opinion of the Investigator, indicates that continued treatment and/or participation in the study is not in the best interest of the patient
- Serious protocol violation, persistent non-compliance or requirement for medication or procedure prohibited by the protocol
- Lost to follow-up

Patients who are terminated early from the study will have an Early Termination visit scheduled as soon as possible (see Section 7.18). All information, including the reason for early termination will be recorded in the patient's study records and in the eCRF.

Two attempts of contact (e.g., telephone contact) followed by a certified letter of contact to the patient must be documented in a patient's study records for all patients who are believed to be lost to follow-up.

8.6.2. Study Drug Discontinuation

Study drug must be discontinued for patients who experience the following:

- Inter-current illness that would, in the judgment of the Investigator, affect assessments of clinical status to a significant degree
- Treatment-related AEs that are clinically significant, deemed persistent, in the judgment of the Investigator
- Unacceptable toxicity
- Pregnancy
- Use of rescue medication as outlined in Section 6.3

Patients who discontinue study drug permanently during study participation must be scheduled for an Early Termination visit (Section 7.18).

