6.3. Treatments for AD

TCS, TCIs and PDE4 inhibitors may be used as needed to treat disease flares during the trial. Patients who may require short-term systemic treatment for symptoms of AD will be assessed on a case-by-case basis and must be discussed with the Medical Monitor prior to initiating treatment.

Cannabinoid treatments for AD are prohibited.

Patients requiring long-term systemic treatment for symptoms of AD (e.g., non-responders) must be discontinued from the study.

Medications used for AD must be recorded in the eCRF.

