7.9. Prior and Concomitant Therapy

Medications will be classified into anatomical therapeutic chemical drug classes using the latest version of the WHO drug dictionary. Medication start and stop dates will be compared to the date of first dose of treatment to be classified as prior or concomitant.

Prior medications are those medications that start and stop prior to the date of first dose of study treatment. *Concomitant medications* are those medications that start before, on, or after the first day of study treatment and continue into the treatment period.

Prior medication and concomitant medication will be summarized by drug class and PT for the safety population.

Rescue medications used during the study treatment period will be presented for the safety population based on the information collected on the *Atopic Dermatitis Treatments* eCRF page. This will include: (1) topical therapy, (2) systemic therapy (e.g., systemic corticosteroids, phototherapy, cyclosporin, etc.). More information on the definition of rescue medications can be found in [Appendix 1](#).

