Appendix 1. Definition of Rescue Medications

This appendix provides the definition of rescue medications for this study, including topical and systemic treatments defined as follows:

1. Topical Atopic Dermatitis Treatment (including corticosteroids, TCI and crisaborole)

Route of topical treatments includes: Topical and Transdermal.

Topical Corticosteroids (TCS): ATC code is D07

High Potency TCS: ATC codes: D07AC or D07AD

Low or moderate potency TCS: ATC code is D07, excluding D07AC or D07AD

Topical calcineurin inhibitor (TCI): Preferred Term includes: TACROLIMUS, PIMECROLIMUS

Crisaborole: Preferred Term includes: CRISABOROLE

2. Systemic Atopic Dermatitis Treatment (including oral corticosteroids, immunosuppressant, biologics and phototherapy/photochemotherapy)

Route of systemic treatments administration includes: Oral, Intra-Arterial, Intramuscular, Intraperitoneal, Intravenous, Subcutaneous, Transdermal. (This condition applies to the following categories except for phototherapies.)

Systemic Corticosteroids: ATC code is H02

Immunosuppressant: Defined as: ATC2 is L04 or Preferred terms of Abrocitinib or Ruxolitinib

Biologics: Defined as following Preferred terms:

Infliximab, Infliximabum, Etanercept, Etanerceptum, Adalimumab, Adalimumabum, Certolizumab, Certolizumabum, Certolizumab pegol, Golimumab, Golimumabum, Ozoralizumab, Afelimomab, Afelimomabum, Tumor Necrosis Factor Alpha (TNF-) Inhibitors, Tabalumab, Tregalizumab, Anakinra, Basiliximab, Basiliximabum, Daclizumab, Daclizumabum, Tocilizumab, Tocilizumabum, Mepolizumab, Mepolizumabum, Riloncept, Rilonceptum, Ustekinumab, Canakinumab, Briakinumab, Fezakinumab, Sirukumab, Sarilumab, Lebrikizumab, Secukinumab, Olokizumab, Gevokizumab, Brodalumab, Ladarixin, Ixekizumab, Dupilumab, Tildrakizumab, Tildrakizumabum, Reslizumab, Reslizumabum, Guselkumab, Guselkumabum, Olamkicept, Fletikumab, Bimekizumab, Mirikizumab, Risankizumab, Abatacept, Ligelizumab, Vedolizumab, Belimumab, Nemolizumab, Tralokinumab, Omalizumab

Phototherapy or Photochemotherapy: Programming search of medication name (actual term or preferred term) contains 'photo' then medicals to manually review to confirm whether the medication in question is indeed 'Phototherapy' or 'Photochemotherapy'

Signature Page for CCI [REDACTED]

Approval	PPD 12-May-2022 15:03:34 GMT+0000
----------	--------------------------------------

Signature Page for CCI [REDACTED]

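### Protocol 8.6.2 makes rescue medication a mandatory reason to stop study drug without naming a type of treatment, which read literally contradicts 6.3 for the topical treatments it permits

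*Protocol*

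**What the plan says.** Protocol 8.6.2 gives a list of events after which study drug must be stopped. The last item is "Use of rescue medication as outlined in Section 6.3". A separate sentence then covers permanent stops: "Patients who discontinue study drug permanently during study participation must be scheduled for an Early Termination visit".

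Protocol 6.3, to which the bullet points, sets out three levels of treatment for atopic dermatitis (AD):

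- **Topical:** "TCS, TCIs and PDE4 inhibitors may be used as needed to treat disease flares during the trial".
- **Short-term systemic:** patients who may need "short-term systemic treatment for symptoms of AD will be assessed on a case-by-case basis", with the Medical Monitor consulted before treatment starts.
- **Long-term systemic:** "Patients requiring long-term systemic treatment for symptoms of AD (e.g., non-responders) must be discontinued from the study".

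Section 6.3 does not use the word rescue. The only definition of rescue medication is in the SAP. SAP Appendix 1 gives the "definition of rescue medications for this study, including topical and systemic treatments", and SAP 7.9 says of the planned summary: "This will include: (1) topical therapy, (2) systemic therapy".

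**The concern.** A mandatory stopping rule points to a section that permits most of what the rule could be taken to cover. The same flare, treated with the same topical corticosteroid, could lead one site to continue dosing under 6.3 and another to stop drug under 8.6.2. If the second site treats the stop as permanent, an Early Termination visit follows.

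As-needed topical use is expressly allowed throughout a 52-week study at about 70 sites, so the situation is foreseeable. Three things are at stake:

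- **Patients:** an adolescent could lose study treatment for doing something the protocol allows.
- **Exposure and disposition:** treatment discontinuations would rise and exposure would shorten, in a study whose first purpose is safety.
- **As-observed efficacy:** SAP 7.3.1 restricts these summaries to patients who have completed treatment up to the visit. Stops prompted by flares would remove flaring patients from later visits, whereas 6.3 keeps them in.

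**Working it through.** The plan states no figure on this point, so the check is mainly a comparison of texts.

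**Step 1. Compare 8.6.2, read literally, with each level in 6.3.**

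| AD treatment | Protocol 6.3 | Literal 8.6.2 | Result |
|---|---|---|---|
| Topical (TCS, TCI, PDE4 inhibitor) | Permitted as needed; no stop | Stop study drug | Contradiction |
| Short-term systemic | Case by case; silent on whether dosing continues | Stop study drug | Unclear |
| Long-term systemic | Discontinue from the study | Stop study drug | Consistent |

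**Step 2. Does the cross-reference limit the bullet to long-term systemic treatment?** That is probably the intention, but three features of the text leave it open:

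- 6.3 never says which of its treatments are rescue.
- The bullet is triggered by use, while the stop in 6.3 is triggered by a need for long-term systemic treatment.
- The only definition of the term, in SAP 7.9 and Appendix 1, includes topicals. It governs reporting and is not an instruction to sites, but it shows that the word is not confined to systemic therapy in this study.

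**Step 3. Which section do the other texts support?** They fit 6.3 for topicals.

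- Protocol 8.6.1 ties early termination to a "requirement for medication or procedure prohibited by the protocol". Topicals used for AD flares under 6.3 are not prohibited.
- SAP 7.3 names rescue treatment as an intercurrent event in its own right, beside treatment discontinuation.
- SAP 7.9 plans a summary of rescue use, topical included, during the treatment period.

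The correction therefore belongs in 8.6.2.

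**Step 4. Short-term systemic treatment.** 6.3 does not say that dosing continues. 8.6.2 deals separately with permanent stops, so its general wording may cover a temporary one. SAP 7.13.1 expects periods of drug interruption with systemic rescue. Holding drug during a short systemic course is compatible with all three, so no contradiction is shown here.

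**Step 5. Illustration for the as-observed summaries (assumed inputs, not an estimate).** Let a share s of 200 patients be stopped for flare treatment. Let r0 be the Week 52 response of the others and r1 the response the stopped patients would have had, with d = r0 − r1. Ignore other dropout.

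- If all are kept: p = (1 − s)·r0 + s·r1. If the stopped patients are removed: p′ = r0.
- Shift: p′ − p = s·(r0 − r1) = s·d.

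| s (assumed) | Patients stopped | n left | Shift for d = 20 points | Shift for d = 40 points |
|---|---|---|---|---|
| 0% | 0 | 200 | 0 | 0 |
| 1% | 2 | 198 | 0.2 points | 0.4 points |
| 5% | 10 | 190 | 1.0 points | 2.0 points |
| 10% | 20 | 180 | 2.0 points | 4.0 points |

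For scale, the asymptotic 95% interval of SAP 7.10, at an assumed 50% response and n = 200, has half-width 1.96 × √(0.5 × 0.5 / 200) = 0.069, or 6.9 points. Every shift in the table is smaller.

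**Step 6. Primary endpoint.** It counts treatment discontinuations due to adverse events. A stop recorded simply as rescue use does not enter it. Protocol 8.4.4.1 requires a pre-existing condition that worsens after dosing to be reported as an adverse event, and SAP 7.13.6.8 tabulates AD exacerbation, so a flare stop could be recorded that way. Each such patient would add 1/200 = 0.5 percentage points.

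**The case against.** The strongest reply is that the bullet is qualified by its reference to 6.3, and 6.3 contains exactly one discontinuation rule, the one for long-term systemic treatment. A specific permission for topicals should override a general cross-reference, and sites do not work from the SAP definition. This is a fair account of what was probably meant. It does not remove the problem, because the mandatory text does not say so and a site applying it as written would stop drug for a permitted treatment.

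A second reply is that the consequence for the analysis is limited. The study is single-arm and descriptive, with no inferential testing. SAP 7.10 and 7.11 also plan summaries after LOCF and MCMC-MI, which can keep stopped patients in; the text of those methods is blacked out, so how they treat such patients cannot be checked. SAP 7.3.1 already acknowledges that the as-observed estimand is conditional on completing treatment and is not causal. SAP 7.6 tabulates treatment discontinuations by primary reason, so these stops would be visible if the reason is recorded accurately. All of this stands. It limits the effect on the reported results, but it does not make the instruction to sites correct.

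A reader might also infer that 8.6.2 contradicts 6.3 for two of its three levels, short-term systemic treatment included. The documents do not support that, for the reasons in Step 4 of the working.

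**Conclusion.** The point holds for topical treatment: a mandatory stopping rule, followed as written, contradicts an express permission. For short-term systemic treatment the protocol is ambiguous, and for long-term systemic treatment the two sections agree.

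The size cannot be estimated. The documents give neither the rate of topical use nor any indication of how many sites would take the bullet literally, and the effect is zero if none do. The illustrative shifts of 0.2 to 4.0 points rest entirely on assumed values of s and d and apply only to the as-observed summaries.

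A reader might infer that the primary endpoint or the efficacy results as a whole are compromised. That does not follow. The primary endpoint is touched only if a flare stop is recorded as due to an adverse event, and the imputed summaries may retain the stopped patients. The correction is still worth making, because the wording governs whether a patient continues treatment and costs almost nothing to put right.

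**What to change.** In Protocol 8.6.2:

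- Replace the bullet with: *Requirement for long-term systemic treatment for AD as outlined in Section 6.3.*
- Add: *Topical treatment permitted by Section 6.3 does not require discontinuation of study drug.*

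Separately, the sponsor should state whether study drug is held during short-term systemic treatment, in a way consistent with the interruption that SAP 7.13.1 expects. The review should not supply that rule, because 6.3 does not contain one.

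The cost is one reworded bullet, one added sentence and one statement from the sponsor, by amendment or clarification letter. No extra patients or procedures are needed. The SAP can stay as it is, since 7.6 already tabulates reasons for discontinuation and 7.13.1 already allows for interruption.

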8.6.3. Data Safety Monitoring Board

An independent data safety monitoring board (DSMB) comprised of members who are independent of the study sponsor and study investigators will monitor patient safety by conducting formal reviews of accumulated safety data.

The DSMB will provide the sponsor with appropriate recommendations on the conduct of the clinical study to ensure the protection and safety of the patients enrolled in the study. The DSMB will also institute any measures that may be required for ensuring the integrity of the study results during the study execution.

All activities and responsibilities of the DSMB are described in the DRM06 DSMB charter.

9. STATISTICAL CONSIDERATIONS

9.1. General Statistical Methodology

9.1.1. Populations Analyzed

All non-PK analyses will be performed using the Safety Population. All patients who receive at least one confirmed dose of lebrikizumab 250 mg will be included in the Safety Population.

The number of patients included in the Safety population will be summarized.

All PK analyses will be performed using the PK population. All patients who are enrolled and have a pre-dose sample and at least one post-dose analyzable sample will be included in the PK population.

9.2. Efficacy Analysis

Efficacy endpoints IGA, BSA, EASI Percent Change from Baseline, EASI-50, EASI-75, and EASI-90 will be summarized by visit.

9.3. PK Analysis

Plasma concentration data will be tabulated and summarized (geometric mean, arithmetic mean, minimum, maximum, SD, and % coefficient of variation) by treatment group for each visit at which samples were taken.

9.4. Anti-Drug Antibody Data Analysis

The ADA variables will be analyzed using descriptive statistics. Positive ADA results may be further evaluated for neutralizing antibodies.

9.5. Immunogenicity Data Analysis

Listings will be provided for immunogenicity data.

9.6. Exposure and Compliance

The extent of exposure to study drug will be summarized by total number of days of exposure, total number of injections, number of missed injections, and number and percentage of patients who are compliant. An injection is considered the full set of injections specified by the protocol.

A patient will be considered compliant with the dosing regimen if the patient received $\geq 75\%$ of the expected number of injections while enrolled in the study.

9.7. Adverse Events

All AEs occurring during the study will be recorded and coded using the Medical Dictionary for Regulatory Activities (MedDRA). Treatment-emergent AEs (TEAEs) are defined as AEs with an onset date on or after the date of the first injection of study drug. TEAEs will be summarized, including the number of patients reporting an event, system organ class, preferred term, severity, relationship to study drug, and seriousness for the safety population. All serious AEs as well as AEs that led to study discontinuation will be listed by patient.

The denominator used for the treatment period will correspond to the number of patients in the safety population. Data will also be corrected for exposure and reported per 100 patient-years.

9.8. Other Safety Data

Laboratory data will be presented in a by-patient listing. Any clinically significant laboratory abnormalities will be captured as AEs. Changes from Baseline in safety laboratory values will be summarized by treatment group at each follow-up evaluation during the treatment period using descriptive statistics or frequency tables as applicable. Tables and listings will be in SAS format. Additionally, changes from Baseline in safety laboratory values will be summarized using shift tables according to normal ranges.

Vital signs will be presented as absolute values and changes from Baseline using descriptive statistics.

Medical histories will be coded using the MedDRA dictionary and presented in a by-patient listing. Concomitant medications will be coded using the World Health Organization drug dictionary. Concomitant medications will be summarized by treatment, drug class, and preferred term. Physical examination data will be presented in a by-patient listing. Growth monitoring of adolescents will be summarized.

9.9. Sample-Size Determination

CCI

9.10. Interim Analyses

Interim analyses may be performed for regulatory interactions, safety updates, and disclosures. A final database lock will be conducted after all patients have either completed the 12 Week follow-up visit for this study, discontinued early or, entered the long-term extension study, DRM06-AD07.

10. ADMINISTRATION

10.1. Compliance with the Protocol

The study shall be conducted as described in this protocol. All revisions to the protocol must be prepared by the Sponsor. The Investigator will not implement any deviation or change to the protocol without prior review and documented approval/favorable opinion from the IRB/IEC of an amendment, except where necessary to eliminate an immediate hazard(s) to study patients. Any significant deviation must be documented and submitted to the IRB/IEC, the Sponsor or designee, and, if required, Regulatory Authority(ies). Documentation of approval signed by the chairperson or designee of the IRB(s)/EC(s) must be sent to the Sponsor and/or designee.

10.2. Informed Consent Procedures

The Informed Consent Form (ICF) will include all elements required by ICH/GCP and applicable regulatory requirements and will adhere to GCP and to the ethical principles that have their origin in the Declaration of Helsinki. The consent form will also include a statement that the Sponsor and regulatory authorities have direct access to patient records.

Prior to the beginning of the study, the Investigator will have the IRB/IEC's written opinion (approval/favorable) of the written informed consent form and any other information to be provided to the patients.

The Investigator must provide the patient or legally acceptable representative with a copy of the consent form and written information about the study in the language in which the patient is most proficient. The language must be non-technical and easily understood. The Investigator should allow time necessary for patient or patient's legally acceptable representative to inquire about the details of the study, then informed consent must be signed and personally dated by the patient or the patient's legally acceptable representative, by the Investigator and/or by the person who conducted the informed consent discussion. The patient or legally acceptable representative should receive a copy of the signed informed consent and any other written information provided to study patients prior to patient's participation in the study.

The informed consent and any other information provided to patients or the patient's legally acceptable representative, should be revised whenever important new information becomes available that is relevant to the patient's consent, and should receive IRB/IEC approval/ favorable opinion prior to use. The Investigator, or a person designated by the Investigator should fully inform the patient or the patient's legally acceptable representative of all pertinent aspects of the study and of any new information relevant to the patient's willingness to continue participation in the study. This communication to the patient should be documented in the source note.

During a patient's participation in the study, any updates to the consent form or to the written information will be provided to the patient in writing.

For patients considered to be minors according to the national legislation in each country, the written consent of the parent or legal guardian must be obtained, as well as the assent of the minor according to his or her capacity to understand the information provided. Patients enrolled as minors who attain legal adulthood during the course of the study must consent in their own right at that time.

